3.6 Subject Study Assessments

Pre-procedure Assessment

A pre-procedure assessment will be performed for each subject enrolled in the study in accordance with standard of care for bronchoscopy procedures. Trained study staff will review the data from available or indicated diagnostic tests confirming the subject's eligibility for study, (i.e. pre- procedure CT scan and laboratory tests), inclusion-exclusion criteria review, and perform an assessment of their medical history. For subjects of child bearing potential, a biochemical (blood or urine) pregnancy test must be obtained prior to the study procedure, per standard practice. If a subject's pre-procedure CT scan was obtained more than 21 days prior to the expected procedure date, a more recent CT scan should be obtained.

Intra-procedure Assessment

Procedure details, including the ability of the investigator to reach a pre-planned target location and obtain a tissue sample will be collected. Procedure durations, such as the total procedure time, anesthesia time, fluoroscopy time and navigation time are among those that will be collected. In addition, the ability to facilitate sampling through the catheter instrument, need for conversion to an alternative biopsy approach or surgery, Rapid On-site Evaluation (ROSE) results and intra- procedural complications (i.e. pneumothorax, bleeding, estimated blood loss and airway damage) will be obtained.

Post-procedure (prior to discharge) Assessment

The following outcomes will be collected: length of stay (bronchoscopy suite or hospitalization) and procedure related complications. Of note, per standard practice, subjects will be required to undergo a chest x- ray at least 1-hour post-procedure but prior to discharge to assess for pneumothorax.

Post-procedure (10 ± 4 days) Assessment

For patients that continue in the study due to a benign or non-diagnostic biopsy. This visit may be completed as a hospital visit, virtual visit or telephone contact. Any potential procedure-related complications will be recorded; in addition, the diagnostic characteristics of the obtained sample, initial pathology result and disease assessment will be obtained. If a subject has undergone any additional diagnostic interventions or treatment related to their pulmonary nodule, data regarding their interventions will be collected for the study but information related to complications will not be collected.

Post-procedure (30 ± 7 days) Assessment

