For patients that continue in the study due to a benign or non-diagnostic biopsy, information related to any additional procedural complications (i.e. pneumothorax or pneumonia) will be collected.

Post-procedure (up to 180 days) Assessment

For patients that continue in the study due to a benign or non-diagnostic biopsy. Pathology and disease information will be obtained from any additional diagnostic assessments, interventions or treatments associated with the study related nodule(s).

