7 ADVERSE EVENTS: LIST AND REPORTING REQUIREMENTS

An adverse event (AE) is any untoward medical occurrence, unintended disease or injury, or untoward clinical signs (including abnormal laboratory findings) in subjects, users or other persons, whether or not related to the investigational medical device. All device and/or procedure related adverse events will be recorded. Events will be collected at the initiation of the index procedure (EBUS), intra-EMN procedures, and for a period of 30 days post-procedure.

Serious Adverse Events (SAE) are those that lead to death or lead to serious deterioration in the health of the subject (i.e. life-threatening injury/illness, permanent impairment of a body structure, leading to prolonged hospitalization). The PI will assess if there is a relationship of an adverse event to the procedure, as related or not related, and categorized as resolved or continuing. Severity of the common complications of pneumothorax and hemorrhage (including hemoptysis) will be classified according to Common

Terminology Criteria for Adverse Events (CTCAE).

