10 STUDY CALENDAR

Baseline evaluations (Standard of Care for Bronchoscopy procedures) are to be conducted within 1 week prior to the procedure. Scans and x-rays are usually done ≤ 3 months prior to the start of procedure, this timeframe will be at the discretion of the PI. If the participant's condition is deteriorating, laboratory evaluations should be repeated within 24 hours prior to initiation of the procedure at the discretion of the PI.

Lab tests taken before the procedure are part of the standard of care. Blood collection will not differ from the usual amounts required for conducting the preanesthetic consultation. A negative blood or urine pregnancy test is required prior to performing the procedure as it involves low dose radiation.

Typical follow-up consultations for standard bronchoscopy procedures are done 1 week. If biopsy is benign or non-diagnostic then the patients will be followed at 4 weeks, and 24 weeks after the procedure but may vary depending on the subject's final diagnosis, underline conditions, further treatment, and PI/Investigator preference.

During the follow-up time, subjects will receive phone calls from the study team to check on the subjects well-being and to remind him/her of any future appointments.

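### The last scheduled complication contact may take place from day 23 and its bracket does not name bleeding, so the 30-day event record that Section 7 requires may be incomplete

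*Combined protocol and SAP*

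**What the plan says.** Section 7 sets the rule for adverse events. Its scope is broad: "All device and/or procedure related adverse events will be recorded". Its period runs from the start of the index procedure "for a period of 30 days post-procedure". On grading it says: "Severity of the common complications of pneumothorax and hemorrhage (including hemoptysis) will be classified", with CTCAE as the scale.

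Section 3.6 sets the schedule. After discharge there is a contact at 10 ± 4 days, at which any potential procedure-related complication is recorded, and then the "Post-procedure (30 ± 7 days) Assessment". The sentence under that second heading is limited to patients with a benign or non-diagnostic biopsy; for them, "information related to any additional procedural complications (i.e. pneumothorax or pneumonia) will be collected". The assessment up to 180 days asks for pathology and disease information and does not mention complications.

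Section 10 describes a typical consultation at 1 week. Patients with a benign or non-diagnostic biopsy are then "followed at 4 weeks, and 24 weeks after the procedure", with timing allowed to vary, among other reasons by investigator preference. It also provides for undated phone calls about well-being and appointments.

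Section 1.3 lists the comparison of complications between groups as a secondary objective. Section 13.6 says that complications will be recorded prospectively, but gives neither a time window nor an event list for that comparison.

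**The concern.** A 30-day complication rate needs each patient to be asked about the whole 30 days, and about the same events. Here the requirement (Section 7) and the schedule that should deliver it (Sections 3.6 and 10) do not match in two respects. The contact that closes the safety period can take place before the period ends. Its bracket also omits one of the two complications that Section 7 singles out for grading.

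Because Section 13.6 defines neither window nor list, the Section 3.6 schedule will in practice shape what is counted. The trial is not blinded, so events that reach the record only by spontaneous report are more open to differences between arms than events asked about with fixed questions on a fixed day. The secondary comparison of complications is at stake. The primary endpoint is not affected.

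**Working it through.** The documents state no figure to reproduce. The check is a comparison of passages with simple day counts.

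**1. Contact window.** Input: 30 ± 7 days (Section 3.6).
- Earliest day: 30 − 7 = 23. Latest day: 30 + 7 = 37.
- Contact on day 23: days 24 to 30 follow it, 30 − 23 = 7 days; 7/30 = 23% of the period.
- Contact at 4 weeks (Section 10): 4 × 7 = day 28, leaving 30 − 28 = 2 days; 2/30 = 7%.
- Contact on day 30 to 37: no gap.

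The gap is thus 0 to 7 days for a patient contacted within the window. An average would need the distribution of contact days, which the documents do not give.

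**2. Is there a later scheduled safety contact?** The next assessment in Section 3.6 (up to 180 days) lists no complications. The Section 10 calls have no dates and are not described as collecting adverse events. No scheduled item therefore covers the days left after an early contact.

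**3. Is bleeding on the list?**

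| Place | Complications named |
|---|---|
| 3.6, during the procedure | a list that includes bleeding and airway damage |
| 3.6, before discharge | procedure-related complications, no list |
| 3.6, 10 ± 4 days | any procedure-related complication, no list |
| 3.6, 30 ± 7 days | pneumothorax or pneumonia, in a bracket |
| 7, 30-day period | all related events; pneumothorax and hemorrhage graded |

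The 10 ± 4 day contact falls on day 6 to 14. For bleeding after that, active collection rests on how the day-30 bracket is read.

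**4. Who has the contact?** Section 3.6 schedules it for patients with a benign or non-diagnostic biopsy. Assume a yield of 67% with NB alone (the meta-analysis figure in Section 13) and 67% + 20% = 87% with CBCT, 68 patients per arm, and a share *b* of diagnostic results that are benign. The documents do not give *b*, so a range is shown. The proportion p(contact) with a scheduled contact is 1 − yield × (1 − *b*).
- *b* = 0: NB alone 1 − 0.67 = 33% (22.4 of 68); CBCT 1 − 0.87 = 13% (8.8 of 68). Without a contact: 136 − 22.4 − 8.8 = 104.8, about 105 of 136 (77%).
- *b* = 0.5: NB alone 1 − 0.67 × 0.5 = 66.5% (45.2 of 68); CBCT 1 − 0.87 × 0.5 = 56.5% (38.4 of 68). Without a contact: 136 − 45.2 − 38.4 = 52.4, about 52 of 136 (39%).

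If yields differ as the trial hopes and *b* is the same in both arms, coverage by this contact differs between arms by 20 percentage points at *b* = 0 and by 10 at *b* = 0.5.

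**The case against.** The strongest reply is that Section 7 is the rule for adverse events and Section 3.6 only a visit schedule. Section 7 asks for all related events over 30 days and nothing in Section 3.6 cancels it. The operative words at the day-30 contact cover any additional procedural complication, and the protocol uses *i.e.* loosely elsewhere, for instance before the intra-procedure list. Section 10 adds phone calls, and its 4 weeks lies inside the 30 ± 7 window. The window and wording are the same in both arms.

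Much of this stands, and it rules out several stronger readings that a reader might infer:
- *Bleeding is excluded at day 30.* The text does not say so. The bracket is ambiguous, not a plain exclusion.
- *Late events are certain to be lost, or the 30-day rates are invalid.* Section 7 still applies, so the documents show a risk of incomplete collection, not a loss.
- *Every patient loses days.* The contact is not scheduled for every patient, and a contact on or after day 30 loses none.
- *Late contacts bring in events from days 31 to 37.* Section 7 fixes the period at 30 days; a later contact date does not extend it.

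The reply does not remove the gap. Section 7 states a requirement but schedules no contact to meet it. The phone calls have no dates and serve well-being and reminders. Someone building the day-30 form from Section 3.6 could reasonably list two items and leave bleeding out. Equal wording in both arms does not ensure equal coverage either, because eligibility for the contact depends on the biopsy result, which is expected to differ by arm.

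**Conclusion.** The point holds as an inexpensive improvement. Following the schedule as written can leave up to 7 of the 30 days (23%) without active complication collection, or 2 days if the contact is at 4 weeks. Late bleeding may be missed if the bracket is taken as the full list. The number of events affected cannot be computed, because the documents give no rate of late events and no distribution of contact days.

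The restriction to benign or non-diagnostic biopsies is an inconsistency with Section 7 that should be reconciled at the same time. Its size depends on the assumed yields and on the unknown share of benign diagnoses. The typical 1-week consultation in Section 10 fills it only in part.

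**What to change.** - **Section 3.6, content:** replace the bracket at the day-30 contact by wording that collects all device- or procedure-related events through day 30, including pneumothorax, hemorrhage/hemoptysis, pneumonia and airway injury.
- **Section 3.6, timing:** hold the planned contact on day 30 to 37, with no tolerance before day 30.
- **Section 10:** align the 4-week follow-up with that window.
- **Section 13.6:** state that the 30-day comparison counts only events with onset on or before day 30, and record onset dates.
- **Sections 3.6 and 7:** reconcile who is contacted with the unrestricted Section 7 period, so that both arms are ascertained alike.

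The first four changes cost a few lines of text and a few items on a contact already planned; the downside is that some contacts take place a few days later. If the last is met by contacting all randomized patients, it adds a contact for about 52 to 105 patients under the assumptions above.

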4. REGISTRATION AND RANDOMIZATION PROCEDURES

4.1 General Guidelines for DF/HCC Institutions

Chest Disease Center will register eligible subjects in the Clinical Trials Management System (CTMS) OnCore. Registrations will occur prior to the initiation of any protocol-specific therapy or intervention. Any subject not registered to the protocol before protocol-specific therapy or intervention begins will be considered ineligible and registration will be denied.

An investigator will confirm eligibility criteria and a member of the study team will complete the protocol-specific eligibility checklist.

Following registration, subjects may begin protocol-specific therapy and/or intervention. Issues that would cause treatment delays should be discussed with the Principal Investigator (PI).

If the subject does not receive protocol therapy following registration, the subject must be taken off study in the CTMS (OnCore) with an appropriate date and reason entered.

4.2 Registration Process for DF/HCC Institutions

N/A

4.3 General Guidelines for Other Investigative Sites

N/A

4.4 Registration Process for Other Investigative Sites

N/A

5. TREATMENT AND/OR IMAGING PLAN

5.1. Treatment Regimen

N/A

5.2. Pre-Treatment Criteria

N/A

5.3. Agent Administration

5.3.1. CTEP and/or CIP IND Agent(s), or other IND agent

N/A

5.3.2 Other Agent(s)

N/A

5.3.3 Other Modality(ies) or Procedures

N/A

5.3.4 Investigational Imaging Agent Administration

Image Acquisition Details:

SuperDimension:

The SuperDimension navigation system version 7.2 with fluoroscopic navigation technology (Medtronic, Minneapolis, MN) is a minimally invasive approach to guide endoscopic tools to difficult to reach lung nodules or masses. The fluoroscopic navigation module incorporates a proprietary advanced algorithm that uses tomosynthesis to reconstruct a 3-dimensional model from multiple 2-dimensional C-arm fluoroscopic images taken at various angles around the patient. Operators are also able to scroll through multiple fluoroscopic slices from different angles, minimizing the impact of any visual obstructions. This method provides enhanced visualization of nodules that might not have been visible on standard fluoroscopy. A local registration feature updates the relationship between the catheter tip and the target intra-procedurally, thus helping to correct CT-to-body divergence.

Ion Endoluminal System:

The Ion™ Endoluminal System assists the user in navigating a catheter and endoscopic tools in the pulmonary tract using endoscopic visualization of the tracheobronchial tree for diagnostic and therapeutic procedures. The Ion™ Endoluminal System enables fiducial marker placement. It does not make a diagnosis and is not for pediatric use. The Ion™ Endoluminal System, Model IF1000, is a software-controlled, electro-mechanical system designed to assist qualified physicians to navigate a catheter and endoscopic tools in the pulmonary tract using endoscopic visualization of the tracheobronchial tree for diagnostic and therapeutic procedures.

The cone beam CT (CBCT) is a high-resolution 2D detector adapted for use with a C-arm. During the procedure, imaging will be performed using angiographic system (XperCT Dual P- Cone beam CT tool, Philips) equipped with a 40×30 cm detector. The CBCT imaging protocol (DynaCT) will be characterized by the following parameters: 8 s rotation time, 200° gantry rotation, 0.5°/projection, 396 total projections, and a detector dose of 0.36 µGy/frame. Using 3D cross section images, the target will be identified and manually contoured on workstation in multiple orthogonal planes using dedicated software (OncoSuite; Philips), and then superimposed on live fluoroscopy to provide real time imaging. Two dedicated holders attached to the bronchoscopy will be utilized to hold the bronchoscope in position so that the operators can leave the room during CBCT scan.

5.4. Definition of Dose-Limiting Toxicity (DLT)

N/A

5.5 General Concomitant Medication and Supportive Care Guidelines

N/A

5.6 Duration of Follow Up

Subjects with a benign / non-diagnostic biopsy may be followed for 24 weeks after the procedure. Subjects removed from protocol therapy for unacceptable adverse event(s) will be followed until resolution or stabilization of the adverse event

5.7 Criteria for Taking a Subject Off Study

Subjects will be removed from study when any of the following criteria apply:

- Lost to follow-up
- Withdrawal of consent for data submission
- Death
- If there is a predetermined plan to pursue stereotactic body radiation therapy (SBRT) in the event of a non-diagnostic study procedure in patients with a nodule in the outer 1/3 lung zone (i.e. The patient would not go on for a CT guided TTNA).
- If there is a predetermined plan to pursue SBRT in the event of a non-diagnostic study procedure in patients where the target nodule is within a region considered to be not accessible to a percutaneous approach as determined by the radiology core lab and thus would prevent a confirmatory tissue diagnosis before SBRT.

The reason for taking a subject off study, and the date the participant was removed, must be documented in the case report form (CRF). In addition, the study team will ensure the subject's status is updated in OnCore.

6 DOSING DELAYS/DOSE MODIFICATIONS

N/A

7 ADVERSE EVENTS: LIST AND REPORTING REQUIREMENTS

An adverse event (AE) is any untoward medical occurrence, unintended disease or injury, or untoward clinical signs (including abnormal laboratory findings) in subjects, users or other persons, whether or not related to the investigational medical device. All device and/or procedure related adverse events will be recorded. Events will be collected at the initiation of the index procedure (EBUS), intra-EMN procedures, and for a period of 30 days post-procedure.

Serious Adverse Events (SAE) are those that lead to death or lead to serious deterioration in the health of the subject (i.e. life-threatening injury/illness, permanent impairment of a body structure, leading to prolonged hospitalization). The PI will assess if there is a relationship of an adverse event to the procedure, as related or not related, and categorized as resolved or continuing. Severity of the common complications of pneumothorax and hemorrhage (including hemoptysis) will be classified according to Common

Terminology Criteria for Adverse Events (CTCAE).

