1.1 Study Design

- We propose a prospective, randomized, two- arm, single-center nonblinded, controlled clinical trial to evaluate the diagnostic yield of lung biopsy in NB-alone and CBCT-guided NB.
- Randomization schedule will be determined in advance by computer with the intent of a 1:1 randomization scheme.
- For randomization, Block randomization will be used. The block randomization method is designed to randomize subjects into groups that result in equal sample sizes. This method is used to ensure a balance in sample size across groups over time. This was decided based on the limited access to the Cone Beam room, which is available exclusively once a month (the first Friday of each month).
- All bronchoscopies will be performed under general anesthesia and ROSE will be available upon physician request/preference.
- Radial probe-EBUS and fluoroscopy will be utilized in all cases.
- Tissue samples will be obtained using multimodality tools, including cytology brush, fine needle for aspiration, biopsy forceps, and bronchoalveolar lavage.
- NB procedure will be performed per product instructions and the institution's standard practice.

CBCT-guided NB procedure arm:

Following intubation, an inspiratory breath-hold maneuver with the adjustable pressure limiting (APL) valve set at 20 cm H₂O will be performed by the anesthesiology provider. This mimic the inspiratory

breath hold done during a CT scan. During the breath-hold maneuver, CBCT will be performed. A dedicated arm attached to the bronchoscopy cart will be utilized to hold the bronchoscope in position so that the operators can leave the room during CBCT scan. Lung nodules will be highlighted using available software (OncoSuite; Philips) during a process known as segmentation. A bronchoscope will be introduced into the airway and then using NB to navigate to the lesion. Nodule segmentation will be visualized in an overlay with live fluoroscopy. Geometric correspondence of augmented fluoroscopy (AF) will be maintained throughout the case while manipulating C-arm angulation, table position, and image-zoom settings. Final catheter position will then be verified in multiple planes with AF. Additional CBCT scans will be acquired when deemed necessary.

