1.3 Secondary Objectives

- To compare the need of additional diagnostic procedures in both groups.
- To compare navigation success in the CBCT-guided NB group.
- To compare complications between groups

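### Section 7 is inconsistent on whether adverse events judged unrelated are recorded, which leaves the complications comparison exposed to an unmasked relatedness call, mainly for later or less obvious events

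*Combined protocol and SAP*

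**What the plan says.** Section 7 makes three statements on the scope of adverse event data:

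- Its definition covers untoward events "whether or not related to the investigational medical device".
- Its recording commitment is "All device and/or procedure related adverse events will be recorded".
- Its causality step is "The PI will assess if there is a relationship of an adverse event to the procedure, as related or not related".

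Collection starts with the index procedure and runs "for a period of 30 days post-procedure". Section 7 defines a serious adverse event but gives no separate rule for recording such events.

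Section 1.1 describes a "single-center nonblinded, controlled clinical trial". Section 1.3 lists as a secondary objective "To compare complications between groups".

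Section 3.6 adds other routes of capture. For the intra-procedure assessment it lists "procedural complications (i.e. pneumothorax, bleeding, estimated blood loss and airway damage) will be obtained", with no causality condition. All subjects have a chest x-ray before discharge. The day 10 and day 30 assessments are described for patients whose biopsy was benign or non-diagnostic.

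**The concern.** The three statements in Section 7 cannot all be followed. If only related events go into the database, nothing remains to be classed as not related. If the not-related class is meant to be used, the recording sentence is too narrow. Site staff have to choose between these meanings, and the plan does not help them.

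The choice matters because relatedness is a matter of judgement and the person making it knows the arm. If an event is recorded and labelled unrelated, the label can be reviewed and the event counted by arm. If the label decides whether the event is recorded, neither is possible. With 68 patients per arm and few complications expected, a handful of such decisions could change how the comparison reads.

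**Working it through.** The plan gives no assumed complication rate and no figure for misjudged causality, so there is no figure to reproduce. The check is mainly a comparison of sections.

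**1. Does another section commit to recording all events?** None does.

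- Section 3.6, before discharge: complications related to the procedure.
- Section 3.6, day 10: complications that might be due to the procedure. This is wider than Section 7's term but still tied to the procedure.
- Section 3.6, day 30: further procedural complications, with pneumothorax and pneumonia named.
- Section 13.6: procedural complications are recorded prospectively; no method of comparison is given.
- Section 12.2: monitoring follows an institutional policy that is not reproduced. Section 13.4 points back to Section 12.
- Section 13.7.1, evaluation of toxicity: not applicable.

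**2. Is causality assessed by anyone masked to arm?** Section 7 names only the PI. Section 1.1 states that the trial is not blinded. No masked or independent adjudication is described.

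**3. Which events are exposed?**

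- Little exposed: intra-procedural pneumothorax, bleeding and airway damage (collected by type), and pneumothorax before discharge (chest x-ray in all subjects).
- Little exposed as to the fact itself: death while on study. Section 5.7 makes it an off-study reason, with reason and date entered in the case report form. That entry is not an adverse event record with a causality call.
- Partly exposed: pneumonia, which is named at day 30 but only for benign or non-diagnostic patients.
- Exposed: late respiratory or cardiac events, non-fatal serious events, and delayed events after a further procedure.

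The last group deserves a number. Section 3.6 says that complications of additional interventions are not collected, so for a late event someone must decide which procedure caused it. Section 13 takes a 67% yield for navigation alone and aims to detect 20 points more, that is 87%. Expected non-diagnostic results are then:

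- navigation alone: 68 × (1 − 0.67) = 22.4, about 22 patients;
- cone-beam arm: 68 × (1 − 0.87) = 8.8, about 9 patients.

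If non-diagnostic results lead to further procedures within 30 days, the need for that attribution will differ by arm.

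**4. How large could an effect be?** This is an illustration on assumed values only. Let the true complication rate r be the same in both arms of 68. Let a share s of one arm's events be judged unrelated and left unrecorded, and none in the other arm. The spurious difference is r × s and the number of lost events is 68 × r × s.

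| r | Expected events per arm (68 × r) | s = 20%: difference; lost events | s = 40%: difference |
|---|---|---|---|
| 0.02% | 0.01 | 0.004 points; 0.003 | 0.008 points |
| 4.9% | 3.3 | 1.0 point; 0.7 | 2.0 points |
| 10% | 6.8 | 2.0 points; 1.4 | 4.0 points |
| 20% | 13.6 | 4.0 points; 2.7 | 8.0 points |

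The first two rates are the ends of the transbronchial pneumothorax range in Section 2.1. They serve only as placeholders, since pneumothorax is the event least open to this problem. The other two rates and both values of s are assumptions. At s = 0, or with equal s in both arms, the spurious difference is zero.

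**The case against.** The strongest reply is that Section 7 can be read as collecting first and classifying second. Its definition ignores cause, it says that events are collected to day 30, and a related/not-related classification presupposes that both kinds reach the PI. The recording sentence does not contain the word only. On this reading the sentence is loose drafting and nothing is lost.

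This reply defeats a stronger inference that a reader might draw: that every event passes through an unmasked causality filter before any data exist. The documents state no such order, and Section 3.6 captures the main procedural complications by event type. It would also be wrong to infer that a death on study leaves no trace, or that unrelated serious events are hidden from safety monitoring. The first conflicts with Section 5.7. The second turns on an institutional policy that the documents do not contain.

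It can also be said that complications are by nature linked to the procedure, that the objective is secondary, and that the primary endpoint is unaffected. All of that is correct and limits the weight of the point.

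The inconsistency itself remains. The only explicit recording commitment covers related events, the relatedness limit recurs in Sections 3.6 and 13.6, and no sentence requires that an unrelated event, even a serious one, be kept. The benign reading is possible, but nothing obliges a site to follow it.

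**Conclusion.** The point holds as an inconsistency with a limited consequence. Section 7 does not settle whether events judged unrelated are kept, and the only named judge of relatedness knows the arm. The between-arm comparison of complications is therefore exposed to an unmasked judgement, chiefly for late respiratory and cardiac events, non-fatal serious events and delayed events after a further procedure.

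Neither the size nor the direction of any bias can be estimated from the documents. The illustrative table depends wholly on assumed rates and an assumed one-sided loss, and should not be read as a forecast. The documents do not show that bias will occur; they show that, if the recording sentence is followed as written, it could not be detected afterwards. The correction is cheap and should be made, as an improvement to a secondary safety comparison.

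**What to change.** Reword the recording sentence in Section 7. Within the 30-day window already stated there, record all serious adverse events and deaths, and all pneumothorax, bleeding, pneumonia, respiratory, cardiac and airway events, whatever the cause. Enter the PI's related/not-related call as a separate field. For the objective in Section 1.3, compare arms on all recorded events and show related events alongside.

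Reconcile Sections 3.6 and 10 with Section 7 at the same time. Section 7 sets a 30-day window without restriction, whereas Section 3.6 describes the day 10 and day 30 assessments, and Section 10 the 4-week follow-up, only for benign or non-diagnostic patients. Without this step the new sentence would not reliably capture later events in patients with a malignant diagnosis, and capture would depend on the biopsy result. Contacts or records already part of routine care could serve, for example.

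The cost is one reworded sentence, one case report form field, and some effort to obtain day-30 information on patients who now have no described assessment then. No additional assessor is needed. The downside is that some background events enter both arms and slightly dilute the comparison; showing related events alongside keeps the narrower view available.
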